6.3.2. Additional considerations

Considering that RCC are available and the percentage of subjects with titres/concentration above key thresholds are available, the distribution of antibody concentrations or titres of each antigen will not be tabulated.

In addition to the percentage of seroprotected or seropositive subjects, the percentage of subjects above the following cut-off will be summarized

- Anti-PRP antibody concentrations $\geq 1.0 \mu\text{g/mL}$.
- Anti-diphtheria antibody concentrations $\geq 1.0 \text{ IU/mL}$.
- Anti-tetanus antibody concentrations $\geq 1.0 \text{ IU/mL}$.
- Anti-HBs antibody concentrations $\geq 100 \text{ mIU/mL}$.
- Anti-pneumococcal serotypes (1, 3, 4, 5, 6A, 6B, 7F, 9V, 14, 18C, 19A, 19F, 23F) $\geq 0.35 \mu\text{g/mL}$.

In light of the number of subjects enrolled in each country, the analysis by country will be replaced with analysis by schedule (2 doses ie 2,4 months combined with 3,5 months versus 3 doses i.e. 2,3,4 months combined with 2,4,6 months).

In addition subgroups analysis according to gestational age (27-32 weeks and 33-36 weeks) and age of the mother (18-24 year, 25-34 year and 35-45 year) will be performed.

The sub-group analyses will be limited to descriptive tables of GMT/GMC and the percentage of subjects with titres/concentration above key thresholds for ATP cohort of immunogenicity.

SCHEDULE_TXT(Element Text)	country(CTY_NAM)						Total
Frequency Percent Row Pct Col Pct	Australia	Canada	Czechia	Finland	Italy	Spain	
Age group(2, 3, 4 Months)	0 0.00 0.00 0.00	0 0.00 0.00 0.00	71 11.81 100.00 100.00	0 0.00 0.00 0.00	0 0.00 0.00 0.00	0 0.00 0.00 0.00	71 11.81
Age group(2, 4 Months)	0 0.00 0.00 0.00	0 0.00 0.00 0.00	0 0.00 0.00 0.00	0 0.00 0.00 0.00	0 0.00 0.00 0.00	7 1.16 100.00 2.48	7 1.16
Age group(2, 4, 6 Months)	38 6.32 8.32 100.00	144 23.96 31.51 100.00	0 0.00 0.00 0.00	0 0.00 0.00 0.00	0 0.00 0.00 0.00	275 45.76 60.18 97.52	457 76.04
Age group(3, 5 Months)	0 0.00 0.00 0.00	0 0.00 0.00 0.00	0 0.00 0.00 0.00	52 8.65 78.79 100.00	14 2.33 21.21 100.00	0 0.00 0.00 0.00	66 10.98
Total	38 6.32	144 23.96	71 11.81	52 8.65	14 2.33	282 46.92	601 100.00

Deviations from specifications for age and intervals between study visits for subjects vaccinated with *Infanrix hexa* by dose schedule (2 dose schedule and 3 dose schedule separately) will be tabulated.

6.4. Analysis of safety

6.4.1. Analysis of safety and reactogenicity planned in the protocol

The primary analysis will be based on the TVC. If more than 5% of enrolled subjects are excluded from the ATP cohort for analysis of safety, then a second analysis based on this ATP cohort will be performed to complement the TVC analysis. All analyses will be descriptive.

- The percentage of doses and of subjects with at least one local symptom (solicited or unsolicited), with at least one general symptom (solicited or unsolicited) and with any symptom (solicited or unsolicited) during the 4-day (Day 0-Day 3) solicited follow-up period will be tabulated with exact 95% CI [Clopper, 1934] after each vaccine dose and overall. The same calculations will be done for symptoms (solicited or unsolicited) rated as grade 3 in intensity, for symptoms (solicited or unsolicited) leading to medical advice and for symptoms (solicited or unsolicited) assessed as causally related to vaccination.

- The percentage of doses and of subjects reporting each individual solicited local and general symptom during the 4-day (Day 0-Day 3) solicited follow-up period will be tabulated after each vaccine dose and overall, with exact 95% CI [Clopper, 1934]. The same calculations will be done for each individual solicited symptom rated as grade 3 in intensity and for each individual solicited symptom assessed as causally related to vaccination.
- All computations mentioned above will be done for grade ≥ 2 (solicited symptoms only) and grade 3 symptoms, for symptoms considered related to vaccination (general symptoms only) and for symptoms that resulted in a medically-attended visit.
- Occurrence of fever and related fever will be reported per 0.5°C cumulative temperature increments as well as the occurrence of grade 3 fever ($> 39.0^\circ\text{C}$ axillary temperature) with causal relationship to vaccination.
- The verbatim reports of unsolicited AEs will be reviewed by a physician and the signs and symptoms will be coded according to MedDRA. Every verbatim term will be matched with the appropriate Preferred Term. The percentage of subjects with unsolicited AEs occurring within 31-day (Day 0- Day 30) follow-up period after any dose with its exact 95% CI [Clopper, 1934] will be tabulated by group, and by preferred term. Similar tabulation will be done for unsolicited AEs rated as grade 3, for unsolicited AEs with causal relationship to vaccination and AEs/SAEs leading to withdrawal from the study.
- The percentage of subjects who receive concomitant medication and antipyretic medication during the 4-day (Day 0- Day 3) follow-up period and the 31-day follow-up (Day 0 – Day 30) will be tabulated (with exact 95% CI [Clopper, 1934]) after each vaccine dose and overall.
- SAEs reported from first vaccination dose up to study end will be described in detail.
- Withdrawal due to AEs and SAEs following vaccinations will be described in detail.

Handling of missing data:

- For a given subject and the analysis of solicited AEs 4 days post-vaccination, missing or non-evaluable measurements will not be replaced. Therefore, the analysis of the solicited AEs based on the TVC will include only vaccinated subjects and doses with documented safety data (i.e. symptom screen completed).
- For analysis of unsolicited AEs, such as SAEs or AEs by primary Medical Dictionary for Regulatory Activities (MedDRA) term, and for the analysis of concomitant medications, all vaccinated subjects will be considered. Subjects, who do not report the event or the concomitant medication, will be considered as subjects without the event or the concomitant medication, respectively.
- For summaries reporting both solicited and unsolicited AEs, all vaccinated subjects will be considered. Subjects, who do not report the event or the concomitant medication, will be considered as subjects without the event or the concomitant medication, respectively.

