10.8. Analysis of safety

The primary analysis will be based on the TVC. If more than 5% of enrolled subjects are excluded from the ATP cohort for analysis of safety, then a second analysis based on this ATP cohort will be performed to complement the TVC analysis. All analyses will be descriptive.

- The percentage of doses and of subjects with at least one local symptom (solicited or unsolicited), with at least one general symptom (solicited or unsolicited) and with any symptom (solicited or unsolicited) during the 4-day (Day 0-Day 3) solicited follow-up period will be tabulated with exact 95% CI [Clopper, 1934] after each vaccine dose and overall. The same calculations will be done for symptoms (solicited or unsolicited) rated as grade 3 in intensity, for symptoms (solicited or unsolicited) leading to medical advice and for symptoms (solicited or unsolicited) assessed as causally related to vaccination.

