11. ANNEX 1 STANDARD DATA DERIVATION RULE AND STATISTICAL METHODS

11.1. Statistical Method References

- The exact two-sided 95% CIs for a proportion within a group will be the Clopper-Pearson exact CI [Clopper CJ, Pearson ES. The use of confidence or fiducial limits illustrated in the case of binomial. *Biometrika*. 1934; 26:404-413].
- The 95% CI for geometric mean titers/concentrations (GMTs/GMCs) will be obtained within each group separately. The 95% CI for the mean of log-transformed titer/concentration will be first obtained assuming that log-transformed values were normally distributed with unknown variance. The 95% CI for the GMTs/GMCs will be then obtained by exponential-transformation of the 95% CI for the mean of log-transformed titer/concentration.

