11.2.2. Dose number

The study dose number is defined in reference to the number of study visits at which vaccination occurred. More specifically dose 1 refers to all vaccines administered at the first vaccination visit while dose 2 corresponds to all vaccinations administered at the second vaccination visit even if this is the first time a product is administered to the subject.

Relative dose: the relative dose for an event (AE, medication, vaccination) is the most recent study dose given before an event. In case the event takes place on the day a study dose is given, the related dose will be that of the study dose, even if the event actually took place before vaccination. For instance, if an adverse event begins on the day of the study vaccination but prior to administration of the vaccine, it will be assigned to this dose. In case a study dose is not administered and an event occurs after the subsequent study dose (e.g. 3rd study dose), the relative dose of the event will be study dose associated to the subsequent study dose (e.g. dose 3).

The number of doses for a product is the number of time the product was administered to a subject.

The incidence per dose is the number of vaccination visits at which an event (vaccination visit is a visit at which study vaccine was administered) was reported among all vaccination visits.

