Solicited general AEs	All subjects with at least one solicited general AE documented as either present or absent (i.e., symptom screen completed)	All study visits with study vaccine administered and with at least one solicited general AE documented as either present or absent (i.e., symptom screen completed)
Solicited local AEs	All subjects with at least one solicited local AE documented as either present or absent (i.e., symptom screen completed)	All study visits with study vaccine administered and with at least one solicited local AE documented as either present or absent (i.e., AE screen completed)
Unsolicited AEs	All subjects with study vaccine administered	All study visits with study vaccine administered
Concomitant medication	All subjects with study vaccine administered	All study visits with study vaccine administered

11.2.6. Number of decimals displayed:

The following decimal description from the decision rules will be used for the demography, immunogenicity and safety/reactogenicity.

Display Table	Parameters	Number of decimal digits
Demographic characteristics	Mean, median age	1
Demographic characteristics	SD (age)	1
Immunogenicity	GMT/GMC	3 for anti-D, anti-T and anti-PRP 2 for Strepto antigens 1 for anti-PT, anti-FHA and anti-PRN, anti-HBs, anti-Polio 1, anti-Polio 2 and anti-Polio 3
Reactogenicity	Mean, Min, Q1, Median, Q3, Max for duration	1
All summaries	% of count, including LL & UL of CI	1

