dTpa Group = This group will consist of infants born to mothers belonging to the dTpa Group in study 116945 [DTPA (BOOSTRIX)-047]. All subjects in this group will receive *Infanrix hexa* co-administered with *Prevenar 13* according to the routine national immunisation schedule.

Control Group: This group will consist of infants born to mothers belonging to the Control group in study 116945 [DTPA (BOOSTRIX)-047]. All subjects in this group will receive *Infanrix hexa* co-administered with *Prevenar 13* according to the routine national immunisation schedule.

For each dose and overall/subject:

N= number of subjects with at least 1 administered dose

n(%) = number(percentage) of subjects presenting at least 1 type of symptom whatever the study vaccine administered

For overall/dose:

N= number of administered doses

n(%) = number(percentage) of doses followed by at least 1 type of symptom whatever the study vaccine administered

95% CI = exact 95% confidence interval, LL = Lower Limit, UL = Upper Limit

Template 18 Percentage of solicited local symptoms reported during the 4-day (Day 0-3) post-vaccination period following each dose and overall (Total vaccinated cohort)

Symptom	Product	Type	each group									
			dTpa group					Control group				
			N	n	%	95 % CI		N	n	%	95 % CI	
Each dose												
Pain	Total	All										
		Grade 2 or 3										
		Grade 3										
		Medical advice										
	Infanrix hexa	All										
		Grade 2 or 3										
		Grade 3										
		Medical advice										
	Prevenar 13	All										
		Grade 2 or 3										
		Grade 3										
		Medical advice										
Redness (mm)	Total	All										
		> 5.0										
		> 20.0										
		Medical advice										
	Infanrix hexa	All										
		> 5.0										
		> 20.0										
		Medical advice										
	Prevenar 13	All										
		> 5.0										
		> 20.0										
		Medical advice										
Swelling (mm)	Total	All										
		> 5.0										
		> 20.0										
		Medical advice										
	Infanrix hexa	All										
		> 5.0										
		> 20.0										
		Medical advice										
	Prevenar 13	All										
		> 5.0										
		> 20.0										
		Medical advice										
Overall/Dose												
Pain	Total	All										
		Grade 2 or 3										
		Grade 3										
		Medical advice										
	Infanrix hexa	All										
		Grade 2 or 3										
		Grade 3										
		Medical advice										

Symptom	Product	Type	each group											
			dTpa group					Control group						

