			N	n	%	95 % CI		N	n	%	95 % CI			
			LL	UL				LL	UL					
Redness (mm)	Prevenar 13	All												
		Grade 2 or 3												
		Grade 3												
		Medical advice												
	Swelling (mm)	Total	All											
			> 5.0											
			> 20.0											
			Medical advice											
		Infanrix hexa	All											
			> 5.0											
			> 20.0											
			Medical advice											
Prevenar 13		All												
		> 5.0												
		> 20.0												
		Medical advice												
Overall/Subject														
Pain	Total	All												
		Grade 2 or 3												
		Grade 3												
		Medical advice												
	Infanrix hexa	All												
		Grade 2 or 3												
		Grade 3												
		Medical advice												
	Prevenar 13	All												
		Grade 2 or 3												
		Grade 3												
		Medical advice												
Redness (mm)	Total	All												
		> 5.0												
		> 20.0												
		Medical advice												
	Infanrix hexa	All												
		> 5.0												
		> 20.0												
		Medical advice												

Symptom	Product	Type	each group													
			dTpa group					Control group								
			N	n	%	95 % CI		N	n	%	95 % CI					
			LL	UL				LL	UL							
Swelling (mm)	Prevenar 13	All														
		> 5.0														
		> 20.0														
		Medical advice														
	Total	Total	All													
			> 5.0													
			> 20.0													
			Medical advice													
		Infanrix hexa	All													
			> 5.0													
			> 20.0													
			Medical advice													
Prevenar 13		All														
		> 5.0														
		> 20.0														
		Medical advice														

dTpa Group = This group will consist of infants born to mothers belonging to the dTpa Group in study 116945 [DTPA (BOOSTRIX)-047]. All subjects in this group will receive *Infanrix hexa* co-administered with *Prevenar 13* according to the routine national immunisation schedule.

Control Group: This group will consist of infants born to mothers belonging to the Control group in study 116945 [DTPA (BOOSTRIX)-047]. All subjects in this group will receive *Infanrix hexa* co-administered with *Prevenar 13* according to the routine national immunisation schedule.

For each dose and overall/subject:

N= number of subjects with at least 1 documented dose

n(%) = number(percentage) of subjects reporting the symptom at least once

For Overall/dose:

N= number of documented doses

n(%) = number(percentage) of doses followed by at least 1 type of symptom

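### Overall/dose safety rows put Clopper-Pearson intervals on pooled doses as if independent; they would be too narrow for symptoms that are not rare if reactions correlate within infant

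*SAP*

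**What the plan says.** SAP 6.4.1 covers "The percentage of doses and of subjects reporting each individual solicited local and general symptom", and these figures "will be tabulated after each vaccine dose and overall, with exact 95% CI [Clopper, 1934". For any, local and general symptoms, Protocol 10.8 likewise plans percentages of doses and of subjects that "will be tabulated with exact 95% CI [Clopper, 1934] after each vaccine dose and overall". SAP 11.1 names one method: "The exact two-sided 95% CIs for a proportion within a group will be the Clopper-Pearson exact CI".

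The dose-level unit is the vaccination visit. SAP 11.2.2 begins its definition with "The incidence per dose is the number of vaccination visits at which an event", taken over all vaccination visits. The denominator table in SAP 11.2.5 gives, for solicited general events, "All study visits with study vaccine administered and with at least one solicited general AE documented as either present or absent".

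The mock tables follow suit. The Overall/dose block has "N= number of administered doses" in Template 17 and "N= number of documented doses" in Templates 18 and 19, with the interval labelled exact. Template 23 has the same kind of block for concomitant and antipyretic medication. There the 6.4.1 text speaks only of subjects, so the dose-level rows rest on the template and on the per-dose denominator in 11.2.5. Annex 3 calls the mocks illustrative; the governing text is 6.4.1, 11.1, 11.2.2 and 11.2.5.

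Neither document mentions clustering, robust variance, a design effect or within-infant correlation in the current analysis text, and SAP section 9 lists no change on this point.

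**The concern.** Clopper-Pearson guarantees its coverage for independent trials with a common probability. In an Overall/dose row the same infant, usually reported on by the same parent, supplies two or three of the trials. If an infant who reacts to one dose is more likely to react to another, the pooled percentage varies more than the binomial model allows. An interval labelled as exact 95% would then cover less than 95%. Because these analyses are descriptive, the interval is the only statement of uncertainty attached to the row. What is at stake is overstated precision in that row.

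**Working it through.** **1. The plan's own figures.** The documents give no numerical interval for Overall/dose rows. The only exact intervals shown are in Protocol Table 22, with one observation per infant. All 37 rows reproduce to within 0.1 point with ordinary Clopper-Pearson limits, for example 210/300 gives 64.5–75.1, 285/300 gives 91.9–97.2 and 238/238 gives 98.5–100.0. The planned method is therefore the standard independent-trial one.

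**2. Inputs.** The schedule table in SAP 6.3.2 has 601 infants: 71 + 457 = 528 on three doses and 7 + 66 = 73 on two. It is not labelled as the Total Vaccinated Cohort. I assume equal groups and every dose documented. Per group: 264 × 3 + 36 × 2 = 864 doses in 300 infants. The within-infant correlation (rho) and the symptom rates are not in the documents, so both are shown as ranges.

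**3. Design effect.** With m doses per infant, the design effect is 1 + (Σm²/Σm − 1) × rho.

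- Σm² = 264 × 9 + 36 × 4 = 2520, and 2520/864 = 2.917.
- Design effect = 1 + 1.917 × rho: 1.19 (rho 0.1), 1.38 (0.2), 1.58 (0.3), 1.96 (0.5).
- The required width grows by its square root: 1.09, 1.18, 1.25, 1.40.

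At a 50% rate the planned half-width is 3.4 points. Clopper-Pearson on 864 divided by the design effect gives 3.7, 4.0, 4.3 and 4.8 points.

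**4. Coverage.** Beta-binomial simulation, 100,000 runs per cell. Each cell shows coverage in %, planned interval / interval adjusted as described under the fix.

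| Rate | rho 0 | 0.05 | 0.1 | 0.2 | 0.3 | 0.5 |
|---|---|---|---|---|---|---|
| 0.5% | 97.2/97.2 | 96.6/96.9 | 95.9/96.6 | 94.4/96.0 | 92.3/95.0 | 87.9/92.1 |
| 1% | 97.7/97.7 | 97.0/97.5 | 96.2/97.3 | 94.8/96.8 | 93.0/96.1 | 89.5/94.7 |
| 2% | 96.1/96.2 | 95.1/95.9 | 94.2/95.8 | 92.2/95.7 | 90.1/95.6 | 85.8/95.5 |
| 10% | 95.3/95.8 | 94.1/95.5 | 93.2/95.7 | 90.8/95.6 | 88.6/95.7 | 84.2/95.6 |
| 30% | 95.5/95.7 | 94.6/95.5 | 93.2/95.3 | 91.1/95.4 | 89.0/95.5 | 84.7/95.5 |
| 50% | 95.5/95.7 | 94.4/95.4 | 93.5/95.3 | 91.2/95.4 | 89.2/95.5 | 84.9/95.6 |

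**5. Sensitivity.**

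- *Rates that differ by dose.* These make the binomial variance slightly too large. For an assumed 40/30/20% pattern the excess is (0.01 + 0 + 0.01)/3 ÷ (0.3 × 0.7) = 3%, which offsets only a very small rho. A logistic-normal model with rates of 60/50/40% and average correlation 0.31 gives 88.9/95.3.
- *Incomplete documentation.* With 80–95% of doses documented (30% rate, correlation 0.30), planned coverage is 89–90%.
- *Prevenar 13 rows of Template 18.* The multiplier is smaller where infants receive two doses; if all did, the design effect would be 1 + rho.

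**The case against.** The strongest case against is that the size rests on a correlation the documents do not contain. At rho 0.05 coverage is 94–95% for rates of 2–50%, which is negligible, and nothing in the plan shows where this trial lies. That stands: only the conditional statement is established.

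Second, nothing depends on these rows. SAP 6.4.1 and section 7 declare the analyses descriptive, with no test, margin or between-group interval. The same tables carry each-dose and Overall/subject rows, where each infant counts once and Clopper-Pearson is appropriate. In absolute terms, at a 50% rate the half-width is short by 0.3 points at rho 0.1 and 0.9 points at rho 0.3. This limits the point to minor but does not remove it. The plan chooses to print an interval on the row and to call it exact, and valid neighbouring rows do not correct that label.

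Third, a tailored clustered interval may be more machinery than a supplementary row deserves, and it is itself not exact. That is fair, which is why dropping the interval is offered on equal terms.

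**Conclusion.** The point holds in conditional form and is minor. If within-infant correlation is positive, the Overall/dose intervals in Templates 17–19 and 23 would under-cover for events that are not rare. At 10–50% rates, coverage would be about 94% at rho 0.05, 93% at 0.1, 91% at 0.2, 89% at 0.3 and 84–85% at 0.5. Near a 1% rate, Clopper-Pearson conservatism offsets rho up to about 0.2. These figures assume 300 infants and 864 documented doses per group; the multiplier of 1.92 hardly moves with group size.

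A reader might infer that the intervals in this trial are certainly too narrow, or that true coverage is a particular figure such as 89%. The documents give no correlation and no expected symptom rates, so they support neither. A reader might also infer that the safety intervals as a whole, or the safety conclusions, are unsound. They do not support that either: point estimates, each-dose rows and Overall/subject rows are unaffected, and no decision rests on the Overall/dose rows.

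**What to change.** In SAP 6.4.1 and 11.1, add one rule for every Overall/dose row (Templates 17–19 and 23), choosing one of two options:

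- report the percentage of doses without a confidence interval; or
- give a 95% interval that accounts for clustering on infant, by applying Clopper-Pearson limits to an effective sample size.

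For the second option, let infant i have mᵢ doses in the denominator and yᵢ with the event, with n = Σmᵢ and p = Σyᵢ/n. The design effect is the infant-level robust variance of p over the binomial variance, D = Σ(yᵢ − mᵢp)² / [n p(1 − p)]. Floor D at 1, and set it to 1 when 0% or 100% of doses have the event. The effective size is n/D. Every cell keeps an interval; for example, 0 of 864 keeps an upper limit of 0.43%.

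Under either option, remove the word exact from the footnote for those rows, keep plain Clopper-Pearson for each-dose and Overall/subject rows, and list the departure from Protocol 10.8 in SAP section 9.

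The first option costs only wording. The second needs minor programming. Its intervals widen by about 1% if doses are in fact independent, and by about 9–41% for rho 0.1–0.5 at 10–50% rates. It can still under-cover for very rare events with high correlation: about 92% at a 0.5% rate and rho 0.5, against about 88% as planned.

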11.2.5. Safety

For analysis of solicited, unsolicited adverse events such as serious adverse events or adverse events by primary MedDRA term, and for the analysis of concomitant medications, all vaccinated subjects will be considered. Subjects who did not report the event or the concomitant medication will be considered as subjects without the event or the concomitant medication respectively.

For a given subject and the analysis of solicited adverse events within 4 days post-vaccination, missing or non-evaluable measurements will not be replaced. Therefore, the analysis of the solicited adverse events based on the Total Vaccinated Cohort will include only vaccinated subjects for doses with documented safety data (i.e., symptom screen completed). More specifically the following rules will be used:

- Subjects who documented the absence of a solicited adverse events after one dose will be considered not having that adverse events after that dose.
- Subjects who documented the presence of a solicited symptom and fully or partially recorded daily measurement over the solicited period will be included in the summaries at that dose and classified according to their maximum observed daily recording over the solicited period.
- Subjects who documented the presence of a solicited symptom after one dose without having recorded any daily measurement will be assigned to the lowest intensity category at that dose (i.e., 37.5°C for fever or grade 1 for other symptoms).
- Doses without symptom sheets documented will be excluded.
- The intensity of the following solicited adverse events will be assessed as described in the below table

Table 4 Intensity scales for solicited symptoms in infants less than 6 years of age

Adverse Event	Intensity grade	Parameter
Pain at injection site	0	None
	1	Mild: Minor reaction to touch
	2	Moderate: Cries/protests on touch
	3	Severe: Cries when limb is moved/spontaneously painful
Redness at injection site		Record greatest surface diameter in mm
Swelling at injection site		Record greatest surface diameter in mm
Fever*		Record temperature in °C/°F
Irritability/Fussiness	0	Behaviour as usual
	1	Mild: Crying more than usual/no effect on normal activity
	2	Moderate: Crying more than usual/interferes with normal activity
	3	Severe: Crying that cannot be comforted/prevents normal activity
Drowsiness	0	Behaviour as usual
	1	Mild: Drowsiness easily tolerated
	2	Moderate: Drowsiness that interferes with normal activity

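### The composite Day 0-3 symptom tables count a dose with no symptom sheet and no other recorded event as symptom-free, while the individual-symptom tables leave undocumented doses out

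*SAP*

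**What the plan says.** Two missing-data rules apply to the same Day 0-3 diary data.

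- **Solicited symptoms alone.** SAP 6.4.1 does not replace missing data, and the analysis "will include only vaccinated subjects and doses with documented safety data (i.e. symptom screen completed"). SAP 11.2.5 adds: "Doses without symptom sheets documented will be excluded". Its denominator table agrees; for general symptoms it uses "All subjects with at least one solicited general AE documented as either present or absent". Templates 18 and 19 take documented doses as N.
- **Solicited and unsolicited events combined.** SAP 6.4.1, with the same rule in Protocol 10.5, states: "For summaries reporting both solicited and unsolicited AEs, all vaccinated subjects will be considered". Those who report nothing "will be considered as subjects without the event or the concomitant medication, respectively".

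The first safety tabulation in SAP 6.4.1 is of the combined kind. It covers local symptoms, general symptoms and subjects or doses "with any symptom (solicited or unsolicited) during the 4-day (Day 0-Day 3) solicited follow-up period will be tabulated with exact 95% CI", and is repeated for grade 3, medically advised and related symptoms. Its layout is Template 17, where the by-dose and overall/subject rows use "N= number of subjects with at least 1 administered dose" and the overall/dose row uses administered doses.

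SAP 11.2.5 also conflicts with itself. Its first sentence, "For analysis of solicited, unsolicited adverse events such as serious adverse events or adverse events by primary MedDRA term", puts solicited events under the all-vaccinated, non-reporter-is-event-free rule. The next paragraph restricts them to documented doses. The denominator table in that section has no row for combined summaries.

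**The concern.** Composite Day 0-3 rates can be expected to consist largely of solicited symptoms, and these come from diary cards. If a card is missing, the infant's symptoms are unknown. Template 17 nevertheless keeps the dose in the denominator and, unless something was recorded elsewhere, counts it as having no symptom. Other records may fill little of the gap: the footnotes to Protocol Tables 6 to 9 show that the diary card also carries unsolicited safety information, so a lost card can remove both kinds of data.

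Two things are at stake. The composite rates, with exact confidence intervals that treat unknown outcomes as known non-events, may be too low. They may also disagree with Templates 18 and 19 in the same report, to the point that a composite falls below one of its own components.

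**Working it through.** The plan states no return rate, symptom rate or bias for this point, so there is no figure to reproduce. The structure comes from the template footnotes; every rate below is an assumption.

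**Inputs**
- *c*: share of administered doses with a symptom sheet. Template 16 defines this compliance measure but gives no value; assumed 90% to 98%.
- *p*: symptom rate among documented doses; assumed 80% for any symptom and 5% for grade 3.
- *f*: share of undocumented doses with a symptom recorded another way; assumed 0 to 20%.

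**Per-dose rate**
- Documented-dose denominator: *p*.
- Template 17: *c* × *p* + (1 - *c*) × *f*.
- With *f* = 0 this is *c* × *p*, a relative shortfall of (1 - *c*). Any *f* above 0 makes the shortfall smaller.

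| Return *c* | p = 80%, f = 0 | p = 80%, f = 20% | p = 5%, f = 0 |
|---|---|---|---|
| 98% | 78.4% | 78.8% | 4.9% |
| 95% | 76.0% | 77.0% | 4.75% |
| 90% | 72.0% | 74.0% | 4.5% |

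Example: at *c* = 95% and *f* = 20%, 0.95 × 80 + 0.05 × 20 = 76.0 + 1.0 = 77.0%.

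**Scale.** The schedule table in SAP 6.3.2 shows 71 + 457 infants on three doses and 7 + 66 on two. That is at most 3 × 528 + 2 × 73 = 1,730 vaccination visits. At 98% return, about 0.02 × 1,730 = 35 visits over both groups would be undocumented.

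**Disagreement between tables.** With *f* = 0, Template 17 shows a composite below a component in Template 18 or 19 when *c* < (component rate) / (composite rate), both on documented doses.
- Component 80%, composite 82%: below 80/82 = 97.6% return.
- Component 80%, composite 85%: below 80/85 = 94.1%.
- Component 80%, composite 90%: below 80/90 = 88.9%.

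**Overall/subject row.** One documented symptomatic dose is enough to count the infant. Assume three doses, 80% per dose, 95% return, *f* = 0 and full independence.
- True: 1 - 0.20³ = 99.2%.
- Template 17: 1 - (1 - 0.95 × 0.80)³ = 1 - 0.24³ = 98.6%, a loss of 0.6 points against 4.0 points per dose.
- The loss approaches the per-dose size only if the same infants return no sheets at all.

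**Group comparison.** With *f* = 0 and the same *p* in both groups, the artificial difference is *p* × (*c*₁ - *c*₂). It is zero when return is equal. At *p* = 80%, 98% against 95% return would give 78.4 - 76.0 = 2.4 points.

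**The case against.** The case for leaving the tables alone is substantial.

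- **The rule is prespecified and every analysis is descriptive.** This stands: no test or error rate is affected. In a descriptive study, however, the rates and intervals are the result.
- **Non-return is managed and disclosed.** Protocol 5.6.14 has missing cards followed up, Template 16 reports return by dose and group, and SAP 11.2.5 warns that N differs between tables. A reader can therefore judge the effect, but nothing corrects it, and no documented-dose version of Template 17 is planned.
- **The composite is not the endpoint.** This stands. A reader might infer that the main reactogenicity results, grade 3 included, are understated. The documents do not support that. The secondary endpoint in SAP 4.2 is the occurrence of solicited local and general symptoms after each vaccination, and Templates 18 and 19 report it, with grade 3, on documented doses.
- **Restricting N could lose events.** This also stands. The composite includes unsolicited and medically attended symptoms, and some may be recorded for infants without a sheet. The fix has to keep them visible.
- **The conflict in SAP 11.2.5 is largely one of wording.** For solicited-only tables, the specific rules and denominator table that follow settle the matter. They do not settle the combined summaries.

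**Conclusion.** The point holds for the composite Day 0-3 tables only. As written, Template 17 understates per-dose rates by up to (1 - compliance), relative to the documented-dose rate, and can contradict Templates 18 and 19. The upper limit applies when no event is recorded for any dose without a sheet. Calling the result too low also assumes that undocumented doses were followed by symptoms about as often as documented ones; if they really had none, the Template 17 rate would be right.

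The size cannot be established from the documents. At about 98% return or higher it is small: 1.6 points on an assumed 80% rate and 0.1 point on an assumed 5% grade 3 rate. The overall/subject row is generally affected less.

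A reader might also infer that the rule creates a false difference between the dTpa and Control groups. It would do so only if return, or the recording of events outside the sheets, differed by group. The documents give no reason to expect that: both groups receive the same vaccines, and Protocol 5.3 keeps site staff blinded to the maternal allocation.

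**What to change.** 1. In SAP 6.4.1, 11.2.5 and Template 17, report the Day 0-3 composite tables with N equal to doses or subjects with a completed symptom screen. This can be the main version, or a version added beside the all-vaccinated one.
2. List separately any Day 0-3 event recorded for a dose without a sheet, so that none is lost.
3. Add a row for combined summaries to the denominator table in SAP 11.2.5, and delete the word solicited from that section's first sentence.
4. Keep all vaccinated subjects for unsolicited AEs and SAEs. Footnote Template 22 to say that its solicited terms use the all-vaccinated denominator.

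The cost is SAP wording and either a slightly smaller N or one extra set of tables. No new data are needed, and Template 17 already has a separate N column for any, general and local symptoms. The gain is mainly in the per-dose rows. Where missing sheets are scattered across infants, the overall/subject row hardly moves: in the example above, 98.62% / (1 - 0.05³) = 98.63%.
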